Official Study Title: Capsaicin 8% Patch for Spinal Cord Injury Neuropathic Pain

NCT number: NCT02441660

IRB Approval Date: 07.24.2019

Unique Protocol ID: HSC20150322H

Protocol Template Form

Item 1 UTHSCSA	15-322H
Tracking Number	

Item 2 Abstract / Project Summary

Provide a succinct and accurate description of the proposed research. State the purpose/aims. Describe concisely the research design and methods for achieving the stated goals. This section should be understandable to all members of the IRB, scientific and non-scientific.

DO NOT EXCEED THE SPACE PROVIDED.

Purpose/Objectives: Current pharmacologic agents for neuropathic pain (NP) in Spinal Cord Injury (SCI) provide 20-30% pain reduction at best; so there is clear need for research studies on new promising evidence-based therapeutic agents. Animal spinal cord injury models show the Transient Receptor Potential Vanilloid subfamily, member 1 (TRPV1) defunctionalization with capsaicin decreases nociceptor hyperactivity. Human trials are needed to substantiate this effect. Most systemic effects of oral agents often limit tolerability, especially as doses are titrated up to achieved maximum clinical effect. Analgesics that can be applied topically have the potential to largely overcome this problem; the only published study of a topical analgesic in persons with SCI examined low dose capsaicin cream in 8 SCI persons and found efficacy. Thus more studies on topical analgesics are needed in persons with SCI. We propose to conduct the first prospective trial of Capsaicin 8% (C8P) in persons with SCI, with hopes to provide SCI patients and clinicians with evidence for a much-needed alternative topical therapeutic without the systemic effects that often limit tolerability.

Research Design/Plan: Randomized dual balanced 2-sequence 2-treatment, 2-period (each period is 12 weeks long), crossover study; with an additional prospective trial arm

Methods:

Randomized control trial: We will recruit 25 patients with chronic SCI and chronic focal neuropathic pain (>6months) below level of injury who have failed multiple pharmacological agents. Pre-study data collection will include subjective description of pain, baseline visual analog scale (VAS) and numeric pain rating scale (NPRS) values, LANNS pain score survey to accurately determine source of pain is neuropathic in origin, a numerical scale such as World Health Organization Quality of Life- (WHOQOL) brief survey (WHOQOL-BREF) that measures quality of life parameters, subjective SCIM (spinal cord independence measure) scores, SCI specific pain measures (MPI-SCI), and pain diagrams will be obtained on each participant. Written informed consent will be obtained. Each participant will be randomized to one of two sequences:

Sequence 1: C8P application followed by one reapplication of a low dose capsaicin control patch (0.025% Well Patch) (available over the counter)

OR

Sequence 2: Control patch (0.025% Well Patch) followed by one replication of C8P. as indicated in Table 1. Measurements of the primary outcome of pain (VAS) will occur every 2 weeks and all secondary outcomes will be measured at 4,8 and 12 weeks within each period in each sequence.

Substudy: Non-randomized, non-controlled sub-study: We will also have a non-randomized non-controlled sub-study to increase data obtained to help calculate Number needed to treat and minimal clinically important difference for the RCT. Patients with SCI undergoing patch as routine medical treatment for refractory neuropathic pain will be recruited and enrolled immediately after patch application. Subsequently, they will be be followed for a 12 week period using the identical protocol of sequence 1 in the RCT, without reapplication of a control patch.

Clinical Relevance: Potentially giving analgesic pain relief for spinal cord focal peripheral neuropathic pain without the hand strength or dexterity required to open bottles, take oral tablets/capsules, or apply a transdermal patch, cream or ointment on a daily basis.

Item 3 Background

Describe past experimental and/or clinical findings leading to the formulation of your study. For research involving unapproved drugs, describe animal and human studies. For research that involves approved drugs or devices, describe the FDA approved uses of this drug/device in

Capsaicin 8% patch (Qutenza) is an FDA approved treatment for neuropathic pain in post herpetic neuralgia (PHN). After the FDA approval of Qutenza several studies have been published assessing the efficacy and safety in patients with HIV autonomic neuropathy and PHN. In a meta-analysis examining 2057 persons with PHN and HIV-AN, the proportion of responders with relief (>30% improvement in pain lasting from 2-12 weeks) over a 12-week treatment period was 43% in the C8P group and 34% in the control group, a statistically significant difference.

A retrospective review by [name] and [name] pending publication in the American Journal of Physical Medicine and Rehabilitation also supports that Capsaicin 8% patch provided all three patients in the study had complete relief of pain on average after 2 weeks for an average duration of 169 days.

relation to your protocol.	
Item 4	While low dose capsaicin cream has shown efficacy with minimal side effects in radicular pain of 8 SCI
Purpose and rationale Insert purpose, objectives and research questions/hypotheses here. If you cut and paste from another document, make	persons, short dosing intervals (every 1-4 hours) and poor manual dexterity of persons with SCI (e.g., tetraplegia) can impair efficacy and adherence. Thus the novelty of high dose capsaicin is that a single topical application of the C8P for only 1 hour could potentially provide pain relief for 8-12 weeks.
sure the excerpted material answers the question	

Item 5 Study Population(s) Being Recruited In your recruitment plan, how many different populations of prospective subjects do you plan to target? Provide number: 2 e.g., a population can be individuals with type 2 diabetes controlled with diet and/or a population of healthy controls. Or a population can be individuals attending an education program, etc. List each different population on a separate row and provide a short descriptive label: (e.g., normal-healthy, diabetics, parents, children, etc.) To add rows use copy & paste	Identify the criteria for inclusion :	Identify the criteria for exclusion : 4.
Spinal cord injury patients with neuropathic pain for RCT	1. Diagnosis of SCI 2. Neuropathic pain below level of injury 3. Surface area of pain no larger than 2 patches 4. Failed or did not tolerate gabapentin 3600mg/day, pregabalin 600mg/day, capsaicin cream and/or lidocaine cream 5. Skin over painful area intact	 Pain over open wound Previously documented allergy to capsaicin Superficial burn over area of pain Premorbid (before SCI) neuropathic pain HIV/AIDS neuropathy Uncontrolled hypertension or autonomic dysreflexia Previous application of capsaicin patch
Spinal cord injury patients with neuropathic pain for prospective trial arm	 Diagnosis of SCI Neuropathic pain Failed or did not tolerate gabapentin G00mg/day, pregabalin 600mg/day, capsaicin cream and/or lidocaine cream Skin over painful area intact have been prescribed the C8P as routine clinical care treatment 	 Pain over open wound Previously documented allergy to capsaicin Superficial burn over area of pain Premorbid (before SCI) neuropathic pain 6. HIV/AIDS neuropathy Uncontrolled hypertension or autonomic dysreflexia

Item 6

Research Plan / Description of the Research Methods a. Provide a comprehensive narrative describing the research methods. Provide the plan for data analysis (include as applicable the sample size calculation).

Step-by-Step Methods:

RECRUITMENT:

RCT: We will identify 25 patients with chronic SCI from our VA SCI clinic, UH SCI and Rehabilitation Clinics, and/or local SCI population. We will recruit with flyers at the VA and UHS. We will utilize chart review and patient interview to ensure patients) meet inclusion criteria above and have failed multiple pharmacological agents. We will gather demographics, clinical history, and imaging on each patient via chart review. SCI attending [name] or one of the four residents participating in this research- [name], [name], [name], or [name]- will contact patients that are appropriate study subjects regarding recruitment for the study and to invite patients to come an outpatient SCI clinic to consent to participate in this prospective study. Each patient's pain will be classified based on a taxonomy utilized by the validated and reliable International Spinal Cord Injury Pain Basic Data Set (ISCIPDS). The ISCIPDS classifies NP into three groups: "at level", "below level", and "other." 24 "At level" and "below level" pain must be directly related to SCI (central nerve injury) and are the only subjects that will be included in this study. Pain will also be validated with the LANNS pain score survey, which is an accurate tool for validation of pain which is neuropathic in origin.

Substudy: Non- randomized, non-controlled arm: The VA SCI clinic routinely applies the C8P to patients as an off-label treatment for refractory pain control. When a patient has been identified to have had the patch placed, we will consent, enroll him/her and follow him every 2 weeks to collect primary and every 4 weeks to collect secondary outcome data as described in the RCT. We aim to enroll 50 persons in this arm of the trial.

CONSENT:

RCT and substudy:

Patients will be approached in a private outpatient room in the spinal cord injury clinic or inpatient room.or via telephone. Risks, benefits, alternative options will be shared and the subjects will be allowed to ask any questions they may have to ensure they understand the risks, benefits and goal of study.

PRE STUDY DATA COLLECTION:

RCT: Pre-study data including subjective description of pain, baseline VAS, LANNS and NPRS. Pre-study data collection will include an intake form with subjective description of pain, baseline VAS / LANNS/NPRS, a numerical scale such as SF36 that measures quality of life parameters, subjective FIM scores, and pain diagrams will be obtained on each participant via the outpatient spinal cord injury clinic, or inpatient spinal cord injury unit.

Substudy: Non randomized, non-controlled arm: no pre-study data collection.

RANDOMIZATION: (RCT only)

Randomized dual balanced 2-sequence 2-treatment, 3-period, crossover study (see Table 1).

Tale 1. The proposed study layout

	Period	
Sequence	1	2
1	Α	В
2	В	Α

Where A indicates 8% Capsaicin and B indicates Low dose capsaicin control patch [1]. Each treatment period will be 12 weeks in duration. The proposed design is a standard 2-period, 2-treatment, 2-sequence design. Inclusion criteria: >1year post SCI, chronic neuropathic pain with VAS>3, pain below the level of injury and failure of at least 3 oral or topical pharmacological agents. Exclusion criteria: painful area >1120cm² (4 patches), skin breakdown over area and uncontrolled hypertension.

Methods:

RCT: Each participant will be randomized to one of two sequences:

Sequence 1: C8P application followed by one reapplication of a low dose capsaicin control patch (0.025% Well Patch) (available over the counter)

ÒR

Sequence 2: Control patch (0.025% Well Patch) followed by one replication of C8P, as indicated in Table 1.

Patch application method: Per manufacturers' application directions, the painful area will be treated with topical lidocaine

2.5%/prilocaine 2.5% for 1 hour prior to application of the test patch(es). Active and control patches will then be applied and left in place for one hour. After removal, the cooling gel will be applied to decrease any burning sensation from the capsaicin, per manufacturers' protocol. Blood pressure will be monitored every 30minutes after the capsaicin (control or treatment) patch over the hour of application.

Substudy: Non-randomized, non-controlled prospective arm: Patients with SCI undergoing patch as routine medical treatment for refractory neuropathic pain will be recruited and enrolled immediately after patch application. Subsequently, they will be followed for a 12 week period using the identical protocol of data collection post patch application in the RCT, without reapplication of a control patch.

Post patch application data collection (RCT and substudy): Measurements of the primary outcome (VAS) will occur every 2 weeks and all secondary outcomes will be measured at 4, 8 and 12 weeks within each period in each sequence. Every 2 week VAS scores will be collected via phone at weeks 2,6,10 and in person at weeks 4, 8, 12. All secondary outcomes surveys will be done at a face to face visit at weeks 4, 8, 12.

Outcome measures: (RCT and substudy)

: Primary efficacy endpoint is the visual analog scale (VAS) score at the end of each of the three 12-week periods (at weeks 12 and 24). Secondary outcome measures include the Multidimensional Pain Inventory (MPI) Pain Severity Subscale, MPI-SCI, International SCI Pain Basic Data Subset (SCIPBDS), WHOQOL-BREF, Spinal Cord Independence Measure (SCIM) and number of concomitant pain medications

Specific Aims

- 1. Determine the effect of the capsaicin 8% patch on VAS scores.
- 2. Determine the effect of the 8% Capsaicin (C8P) on QOL.
- 3. Determine the effect of the C8P on physical function. .

UHS clinic sites: Patients will be approached by providers (who are also investigators in this study), regarding being contacted by phone to hear more about the study. If agreeable patient's name and phone number will be provided manually/verbally to the study team at the VA in order to contact interested patients. No PHI will be transferred electronically between UHS and the VA. Data for the study will be provided by patient and collected at the VA.

Data Analysis Plan:

RCT: Due to the small population of individuals with a spinal cord injury and high incidence of neuropathic pain in such persons and lack of prospective studies on the capsaicin 8% patch, we felt a small group of 25 patients was large enough to show possible potential benefits, small enough to realistically complete this study, follow patients appropriately according to standard of care, and in congruence with the small population size commonly seen in spinal cord injury studies. This study will serve as pilot data for a larger study in the future.

Substudy: Non-randomized, non-controlled arm: 50 participants will be enrolled and we will use the baseline and post patch application data to help determine the number needed to treat and minimal clinically important difference for the RCT.

RCT and substudy: Data analysis will be performed on subjective description of pain at baseline from NPRS, VAS and evaluated at 2, 4, 8, 12 weeks post application to determine efficacy of capsaicin 8% patch in regards to point value and percentage of reduction compared to baseline. Longevity as recorded by reduction in baseline NPRS and VAS scores in days, weeks, and months of relief until pain returns to baseline. We will also compare our quality of life scale (WHO-QOL) and SCIM scores from pre study to post study and evaluate for more subjective measures of improvement in quality of life and functional improvement respectively. In the RCT trial we will assess for significant differences is outcomes between the treatment and control groups over time whereas, in the non-randomized, non-controlled trial we will compare baseline scores to 12 weeks post patch application scores for all outcomes. The significance of variation in the mean outcome with treatment will be assessed with a mixed effects linear model of the outcome in terms of sequence, subject nested in sequence, period, treatment, and first order carryover. All statistical testing will be two-sided with a significance level of 5%. SAS Version 9.4 for Windows or later, SAS Instititue, Cary, North Carolina, or R will be used throughout.

0

15-322H, [name], Form BC, 07-24-19, AMD.docx vSept3-2014

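### The substudy's before-after analysis needs baseline scores that the protocol says are not collected, and the plan does not say how an uncontrolled arm would inform the RCT's number needed to treat (NNT)

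*Combined protocol and SAP*

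**What the plan says.** The protocol gives the substudy its purpose in two places. Item 2 describes "a non-randomized non-controlled sub-study to increase data obtained to help calculate Number needed to treat and minimal clinically important difference for the RCT". The Data Analysis Plan in Item 6 says of the 50 participants that "we will use the baseline and post patch application data to help determine the number needed to treat and minimal clinically important difference".

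On what is collected and when, Item 6 under pre-study data collection reads "Substudy: Non randomized, non-controlled arm: no pre-study data collection". Item 6 under Recruitment reads "When a patient has been identified to have had the patch placed, we will consent, enroll him/her". Item 2 and the Methods part of Item 6 also place enrolment directly after application.

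On analysis, the Data Analysis Plan says that "in the non-randomized, non-controlled trial we will compare baseline scores to 12 weeks post patch application scores for all outcomes". In text covering both the RCT and the substudy, it also plans to "compare our quality of life scale (WHO-QOL) and SCIM scores from pre study to post study".

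No formula, responder definition or control rate is given for the NNT, and no method or anchor for the MCID. The only responder rates in the document are background figures in Item 3 from post-herpetic and HIV-related neuropathy: "improvement in pain lasting from 2-12 weeks) over a 12-week treatment period was 43% in the C8P group and 34% in the control group".

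**The concern.** A before-after comparison needs a before. If no pre-application score is collected and the plan names no other source, the substudy's only stated comparison has no defined starting value. Percentage reduction, responder status and any MCID based on change scores all depend on that value.

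The NNT raises a different problem. It is the reciprocal of a difference in response between treated and control patients, and a cohort in which everyone receives C8P contains no such difference. The substudy could contribute only in combination with other data, and the plan does not describe the combination. If substudy responses were merged with the RCT's C8P responses, readers could take a largely non-randomised figure for a randomised effect.

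**Working it through.** **Baseline: the statements side by side**

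- Collected before the study: nothing for the substudy (Item 6, pre-study data collection).
- Time of consent: after the patch has been placed (Item 6, Recruitment; likewise Item 2 and Item 6, Methods).
- Required by the analysis: baseline and post-application data (Data Analysis Plan, Substudy), and baseline against week 12 for every outcome (Data Analysis Plan, RCT and substudy).
- Other source named: none. The chart review in Item 6 stands under the RCT heading.

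The first two statements leave no prospectively collected pre-patch score, and the third requires a baseline. The before-after comparison for the 50 participants therefore cannot be run as written. A score taken at enrolment would follow the patch. If routine application uses the method described in Item 6, it would also follow an hour of topical anaesthetic, so it would not be a clean pre-treatment VAS.

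**NNT: no figure in the plan to reproduce**

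The plan states no NNT, so what follows is illustration only. Inputs: 43% and 34% from Item 3, 25 RCT patients and 50 substudy patients. The rates come from another population, and their responder definition differs from a week-12 endpoint.

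1. NNT = 1/(treated rate − control rate) = 1/(0.43 − 0.34) = 11.1. Without subtracting a control rate, 1/0.43 = 2.3. The control rate matters a great deal.
2. If the two sources were pooled, the non-randomised share would be 50/(25 + 50) = 50 of 75.
3. Pooled C8P rate = (25 × 0.43 + 50 × s)/75, where s is an assumed substudy response rate, and control is 34%:

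| s | Pooled rate | NNT |
|---|---|---|
| 35% | 0.377 | 27.3 |
| 40% | 0.410 | 14.3 |
| 43% | 0.430 | 11.1 |
| 50% | 0.477 | 7.3 |
| 60% | 0.543 | 4.9 |

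The pooled difference reaches zero at s = (0.34 × 75 − 10.75)/50 = 0.295. Bias can go either way and is absent at 43%. One reason the two groups may differ is in Item 5, which excludes previous capsaicin-patch users from the RCT but not from the substudy.

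**Precision of an NNT from the RCT alone**

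Assume 43% v 34%, 25 complete pairs split 12/13, no carryover, and the within-patient difference averaged over the two sequences.

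- Variance of a within-patient difference: Vd = 0.43 × 0.57 + 0.34 × 0.66 − 2φ√(0.43 × 0.57 × 0.34 × 0.66), where φ is the within-patient correlation.
- SE = √[Vd(1/12 + 1/13)/4], with t on 23 df = 2.069.
- φ = 0: SE 0.137; 95% CI 0.09 ± 0.284, or −19 to +37 points.
- φ = 0.5: SE 0.097; 95% CI 0.09 ± 0.201, or −11 to +29 points. As an NNT this runs from 1/0.291 = 3.4 through infinity to a number needed to harm of 1/0.111 = 9.0.

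In 200,000 simulated trials at each correlation, the interval lay wholly above zero in about 9% (φ = 0) to 19% (φ = 0.7) of trials. With an assumed control rate of 20%, the figure was about 40% (φ = 0) to 73% (φ = 0.5).

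**The case against.** The strongest reply on the baseline is that it is undefined rather than impossible. Clinic records may hold pre-application pain scores. A score taken at enrolment might serve for quality of life, SCIM or medication count, even if not for VAS. Item 2 also says the substudy follows the protocol of sequence 1, which could be read to include its baseline. The first two possibilities stand, since the documents do not rule them out. The last is weak, because the Methods part of Item 6 limits the shared protocol to data collection after application. A reader might infer that no responder rate could ever be formed for these 50 patients. The documents do not support that; they show only that the plan names no source.

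On the NNT, the reply is that the purpose is only to help, that the RCT has its own control patch, and that neither pooling nor the reciprocal of a single-arm response rate is proposed anywhere. This also stands. A reader might infer that the sponsor intends a pooled or uncontrolled NNT, but the text does not say so. What remains is that the NNT is a stated purpose with no stated method, and that the substudy alone cannot meet it.

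**Conclusion.** The baseline contradiction is direct and rests on the text alone. As written, the before-after comparison lacks a starting value for all 50 substudy participants and for every outcome it covers. How much could be rescued depends on whether pre-application scores exist, which the documents do not say.

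The NNT point is a gap in specification, and its consequence is conditional. If the data were pooled, two thirds of the C8P responses would be non-randomised, with bias of unknown direction. The numerical examples rest on assumed substudy rates and on responder rates from another population, so they show sensitivity and do not predict this trial. MCID shares the gap: it is paired with the NNT in both statements of purpose, draws on the same undefined baseline and has no anchor.

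The stakes are limited. Neither NNT nor MCID is among the three specific aims or the listed outcomes, the RCT is described as pilot work, and its mixed-model treatment test does not use substudy data. The plan should be corrected, but the point does not threaten the trial's main result.

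**What to change.** 1. Reconcile the pre-study data collection text in Item 6 with the Data Analysis Plan. For each outcome, state the source and timing of the substudy baseline: for example, pre-application clinic records, or scores collected before application in patients already prescribed the patch (a substudy entry criterion in Item 5). Where no pre-application score exists, drop the before-after comparison for that outcome and report observed scores only.
2. In Item 2 and the Data Analysis Plan, state that any NNT comes only from the RCT's randomised C8P-minus-control difference in responders. Prespecify the responder definition, such as a VAS reduction of more than 30% from the pre-study baseline at week 12 of each period. Report the risk difference with its 95% CI, and describe substudy response separately.
3. Remove MCID from the substudy's purpose for any outcome that lacks a valid baseline and a stated anchor.

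The cost is mostly wording. Scoring before application would mean earlier consent and an extra assessment for future enrolees, and some before-after comparisons may be lost for patients already enrolled. The RCT-only NNT will be imprecise. Under the assumed 43% v 34%, its interval would probably include no difference and so be unbounded, and the report should say so if that happens.

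### The substudy enrols patients after the patch and collects no pre-study data, yet its planned analyses compare week 12 with a baseline that nobody is scheduled to measure.

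*Combined protocol and SAP*

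**What the plan says.** **Timing of entry.** Item 6, Recruitment, describes substudy entry as "When a patient has been identified to have had the patch placed, we will consent, enroll him/her". The substudy paragraphs in Item 2 and in Item 6, Methods, both have patients "recruited and enrolled immediately after patch application".

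**Data before the patch.** Item 6, Pre Study Data Collection, gives the RCT an intake assessment. For the other arm it says: "Substudy: Non randomized, non-controlled arm: no pre-study data collection".

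**Data after the patch.** Item 6, Methods, follows the substudy for 12 weeks "using the identical protocol of data collection post patch application in the RCT". The schedule, headed as applying to both the RCT and the substudy, reads: "Every 2 week VAS scores will be collected via phone at weeks 2,6,10 and in person at weeks 4, 8, 12". It continues: "All secondary outcomes surveys will be done at a face to face visit at weeks 4, 8, 12".

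**Planned analyses.** For the substudy, the Data Analysis Plan says "we will use the baseline and post patch application data to help determine the number needed to treat and minimal clinically important difference". The paragraph covering both parts calls for "point value and percentage of reduction compared to baseline", for the duration of relief until pain is back at its baseline level, and for pre- to post-study change in WHOQOL and SCIM. For the non-randomised arm specifically, it sets baseline scores against week-12 scores on all outcomes.

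**The concern.** Every one of those substudy analyses needs a value from before the patch, and the plan states that none is collected. Followed exactly, it would put 50 people through 12 weeks of calls and visits and could only describe their post-patch scores. The change, percentage reduction and duration of relief that the arm is meant to supply would have no starting point.

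A missed pre-patch score cannot be measured later, and no analysis method restores it. The obvious substitutes are weak:

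- A score taken at enrolment comes after treatment.
- A recalled score is open to recall error.
- The first scheduled VAS, at week 2, may already contain much of the effect. The three-patient retrospective review in Item 3 reports complete relief after 2 weeks on average. That is very small evidence, but it is the protocol's own evidence on onset.

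**Working it through.** The protocol gives no effect size, standard deviation, power or dropout rate for the substudy target of 50, so that figure cannot be reproduced. The check is a count of the measurement schedule.

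**Inputs**

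- Planned sizes: 25 in the RCT and 50 in the substudy (Item 6, Recruitment).
- Outcomes (Item 6, Outcome measures): VAS, plus six secondary outcomes, namely MPI Pain Severity, MPI-SCI, SCIPBDS, WHOQOL-BREF, SCIM and number of concomitant pain medications. Total 1 + 6 = 7.
- VAS times: weeks 2, 4, 6, 8, 10 and 12.
- Secondary outcome times: weeks 4, 8 and 12.
- Substudy scores before the patch: none (Item 6, Pre Study Data Collection).

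**Count**

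1. Post-patch scores per participant: VAS 1 × 6 = 6; secondary 6 × 3 = 18; total 24.
2. Pre-patch scores per participant: 0.
3. A baseline/week-12 pair needs both ends scheduled. Week 12 is scheduled and a pre-patch time is not, so pairs = 50 × 0 = 0 for VAS and 0 for each secondary outcome.
4. Over all seven outcomes: 0 of 50 × 7 = 350 planned pairs. Adding NPRS, which the Data Analysis Plan also evaluates, changes only the denominator: 0 of 50 × 8 = 400.
5. Share of all planned participants: 50/(25 + 50) = 66.7%.

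**Could another part of the protocol supply the baseline?**

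- Item 2 says the substudy follows the same protocol as sequence 1. That sentence concerns follow-up after enrolment, and Item 6, Methods, narrows it to collection after the patch.
- The chart review in Item 6, Recruitment, stands under the RCT heading and covers demographics, clinical history and imaging, not outcome scores.
- The VAS entry threshold stands under Randomization, which is marked as RCT only. The substudy criteria in Item 5 contain no pain score.

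**What a baseline would buy.** For a paired mean change, two-sided α = 0.05 and an assumed 80% power, the detectable change in SDs of within-patient change is (1.960 + 0.842)/√n by the normal approximation. The 95% confidence half-width is 1.960/√n. The numbers of usable pairs are assumptions.

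| Usable pairs | Detectable change (SD) | 95% CI half-width (SD) |
|---|---|---|
| 50 | 0.40 | 0.28 |
| 40 | 0.44 | 0.31 |
| 25 | 0.56 | 0.39 |
| 10 | 0.89 | 0.62 |
| 0 | not estimable | not estimable |

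**The case against.** The strongest reply is that the protocol fails to name a baseline source, which does not prove that none exists. These are patients the VA clinic treats routinely, so their records may hold pre-patch pain scores. This stands as a limit on the claim: what is shown is that no pair is *planned*, not that none could ever be found. It does not remove the conflict, because the plan neither names such records nor says which of the outcomes they would cover.

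Second, the harm differs by outcome. A VAS taken after the anaesthetic cream and the patch is plainly compromised. A medication count could be recovered from records, and SCIM is unlikely to shift within hours. That is fair, but no enrolment score is scheduled for any outcome.

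Third, the arm is uncontrolled, has only a supporting role beside a self-described pilot RCT, and would not yield a sound NNT or MCID even with a baseline. This too is correct, and it confines the seriousness to the substudy. Within the substudy, the lost comparison is the only one specific to that arm.

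Fourth, the RCT's own baseline is secure for VAS but less clear for some secondary outcomes: Item 2 lists WHOQOL-BREF, SCIM and MPI-SCI before the study, whereas Item 6 lists SF36 and FIM. That is a separate inconsistency, but it bears on which instruments a new substudy baseline should use.

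**Conclusion.** The concern holds, and for the substudy it must be fixed. The plan contradicts itself: it excludes pre-study data in this arm and then builds the arm's analyses on them. None of the 50 participants has a planned baseline/week-12 pair on any outcome. As written, the baseline-dependent substudy analyses cannot be done, and the baseline input to the NNT and MCID is missing.

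The count rests only on the stated schedule and needs no assumption. The 80% power and the reduced numbers of usable pairs in the table are assumptions and do not affect the conclusion. The RCT's randomised comparison is not touched.

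**What to change.** **Preferred change**

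1. In Item 2 and Item 6, Methods, replace "recruited and enrolled immediately after patch application" with wording to this effect: *consented and enrolled once the capsaicin 8% patch has been prescribed as routine care, and before any pre-treatment or patch is applied*. Amend the consent sentence in Item 6, Recruitment, to match. Prescription as routine care is already a substudy inclusion criterion in Item 5, so clinical care does not change.
2. Delete the statement that the substudy has no pre-study data. At the new pre-patch contact, collect VAS, NPRS and the six secondary outcomes. LANNS, as in the RCT intake, would be a useful addition but is not needed to resolve the conflict.
3. Use the same instruments before and after the patch, settling the WHOQOL-BREF/SCIM versus SF36/FIM discrepancy. List NPRS in the post-patch schedule, since the Data Analysis Plan evaluates it.
4. Define the analysed group as those who then receive the patch.

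**If consent before the patch is not feasible,** either name a documented pre-patch source for each outcome, or restrict the substudy to post-patch description and remove the baseline comparisons from the Data Analysis Plan.

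**Cost.** A consent-timing amendment and one extra questionnaire session, which may need a separate contact when consent is by telephone. Some consented patients may not go on to receive the patch. The protocol gives no rate; if 5% to 20% do not (assumed), 50/0.95 = 52.6 to 50/0.80 = 62.5, that is 53 to 63 consents, are needed for 50 treated.

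**Limit.** This makes the pre/post comparison possible. It does not by itself make an NNT estimable from an uncontrolled arm, nor supply an anchor for the MCID.
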